4.1.1. Primary Objective

The primary objective of this CSR SAP is to evaluate the safety and tolerability of IV administration of SBC-103 in previously studied, SBC-103 treatment naïve subjects with mucopolysaccharidosis III, type B (MPS IIIB, Sanfilippo B) who participated in the NGLU-CL01 study. The NGLU-CL01 study was a non-interventional study that evaluated structural brain abnormalities and blood brain barrier (BBB) integrity by magnetic resonance imaging (MRI) and cerebrospinal fluid/serum albumin index (CSF-AI).

4.1.2. Secondary Objectives

No secondary objectives will be addressed in this SAP.

4.1.3. Exploratory Objectives

No exploratory objectives will be addressed in this SAP.

4.1.4. Assessments / Parameters Included in Analysis

- Demographics
- Disposition
- Use of Prior and Concomitant Medications (Listing only)
- Treatment Exposure, Dosing Administration and Infusion Summary (Listings only)
- Treatment Emergent Adverse Events (TEAEs)
- Treatment Emergent Serious Adverse Events (TESAEs)
- Infusion Associated Reactions (IAR)
- Anti-drug Antibody (ADA) Assay and Titer Results
- Laboratory Parameters: Hematology, Chemistry, Urinalysis, including Coagulation, Renal Function, and Liver Function (Listings only).
- Lumbar Puncture: CSF Findings and CSF-AI Ratio (listings only)
- Vital Signs (listing only)

4.2. Changes from Analyses Specified in the Previous Version of the SAP

Not applicable.

5. **DEFINITIONS**

5.1. Efficacy

5.1.1. **Primary Endpoint(s)**

The primary objective is to evaluate the safety and tolerability of IV administration of SBC-103, and as such, there is no primary efficacy endpoint.

5.1.2. Secondary Endpoints

Analyses of secondary efficacy endpoints will not be included in the CSR.

5.1.2.1. Pharmacokinetic (PK) Parameters

Analyses of PK data will not be included in the CSR.

5.1.2.2. Pharmacodynamic (PD) Parameters

Analyses of PD or PK/PD data, including HS, will not be included in the CSR.

5.1.3. Tertiary Endpoints

Not applicable.

5.1.4. Other Efficacy Endpoints

5.1.4.1. Exploratory Endpoints

Analyses of exploratory endpoints will not be included in the CSR.

5.2. Safety

The primary endpoint of this study is the safety and tolerability of SBC-103 in subjects with MPS IIIB. The safety assessments will include the following:

- Incidence of treatment emergent adverse events (TEAEs), treatment emergent serious adverse events (TESAEs), and infusion-associated reactions (IARs) which are adverse events of special interest (AESI).
- Incidence of anti-drug antibodies (ADA) including ADA titer by time point, peak ADA titer, and ADA titer status (positive/negative), and the effect of ADAs on the safety of SBC-103, including the relationship between ADA-positive subjects and the incidence of IARs.

5.2.1. Adverse Events (AEs)

Adverse events are defined in Protocol Section 7.1. Also refer to Appendix 9.4.3 of this SAP for special handling of AE partial dates. Any AE that occurs after the first dose of SBC-103 is considered a treatment emergent adverse event (TEAE) for this study.

5.2.2. Vital Signs

Vital signs will be provided in a listing. The following vital signs were recorded at the times specified in Appendix 9.1: systolic and diastolic blood pressure (millimeters of mercury (mmHg)), heart rate (beats/minute), respiratory rate (breaths/minute), and temperature (degrees Celsius (°C) or degrees Fahrenheit (°F)).

5.2.3. Laboratory Assessments

Serum chemistry, hematology, urinalysis, including coagulation, renal function, liver function, CSF, and assessment of ADAs related testing will be performed as per the SOA. Details on specific laboratory assessments are provided in Appendix 9.1. All laboratory results will be provided in listings.

5.2.4. Other Safety Assessments of Special Interest

5.2.4.1. Anti-Drug Antibodies (ADA)

Patients will be monitored for the development of antibody production against SBC-103 at the times specified in Appendix 9.1. Serum will be collected and analyzed for the presence of ADA, and if positive, further analyzed for titer, and characterization of response (e.g., positive/negative).

5.2.4.2. ECG

Analyses of electrocardiogram (ECG) data will not be included in the CSR.

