8.4 Safety Analysis

Descriptive statistics will be computed for safety parameters as per FAS, as appropriate. Number and percentage of subjects who discontinued from the study because of AEs, will be tabulated across doses; severity and frequency of AEs and SAEs will also be tabulated across doses. All other safety data will be provided in listings. Baseline (as described in Section 8.3), within study, end of study, and change from baseline in physical examination findings, ECG, clinical laboratory values, and vital signs will be summarised by dose.

The number and proportion (percentage) of subjects with measurable antibodies to SBC-103 will be displayed. In addition, incidence of IARs will be tabulated by dose and overall. Medications to treat IARs, including any pre-treatment medications, will also be presented by dose and for the entire study period. SBC-103 infusions in which the rate was slowed or discontinued due to IARs will be detailed in a separate data listing.

Additional statistical evaluations may be carried out for select endpoints, if warranted. All baseline and safety data collected during the study will be included in subject listings.

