Study NGLU-CL01-T, A Phase I/II Open Label Study in Previously Studied, SBC-103 Treatment Naïve MPS IIIB Subjects to Investigate the Safety, Pharmacokinetics, and Pharmacodynamics/Efficacy of SBC-103 Administered Intravenously, is an open label Phase I/II study designed to evaluate the safety and tolerability of intravenous (IV) administration of SBC-103 in previously studied, SBC-103 treatment naïve subjects with mucopolysaccharidosis III, type B (MPS IIIB, Sanfilippo B) who participated in the NGLU-CL01 study. The NGLU-CL01 study was a non-interventional study that evaluated structural brain abnormalities and blood brain barrier (BBB) integrity by magnetic resonance imaging (MRI) and cerebrospinal fluid/serum albumin index (CSF-AI).

The protocol can be referenced for additional details. The schedule of events is attached in Appendix 9.1 of this Statistical Analysis Plan (SAP).

On 11 Jul 2017, Alexion decided to stop the clinical development program with SBC-103. A clinical study report (CSR) will detail the final demographic, disposition, exposure and safety data of each study.

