4.1. Changes from Analyses Specified in the Protocol

The data analyses, data summaries and data presentations specified for the NGLU-CL01-T CSR represent a reduced subset of the overall total data analyses, data summaries, and data presentations described in the NGLU-CL01-T final approved Clinical Study Protocol (CSP) version (Amendment 2, 24 February 2016) for the full study. Only demographic, disposition, safety and exposure data will be used to create data summaries and listings for the reduced subset of the CSP specified full study parameters. Only the assessments/parameters specified in Section 4.1.4 will be included.

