7.1.3.3. Medical / Surgical History and Baseline Physical Examination

Medical/surgical history and physical examination data will not be included in the CSR.

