7.3.3.3.2. ECG

Analyses of ECG data will not be included in the CSR.

8. **REFERENCES**

Statistical Analysis Plan {01 Sep 2017, Version 1.0}

9. **APPENDICES**

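### The SAP keeps safety and tolerability as the primary endpoint but gives two of its seven protocol components, ECG and physical examination, neither a table nor a listing, and drops seroconversion without naming it

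*SAP*

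**What the plan says.** Protocol 3.4.1 makes safety and tolerability the primary endpoint and lists seven components: AEs, SAEs and IARs; laboratory tests and CSF findings; 12-lead ECG; vital signs; physical examination; concomitant medications; and ADA. The ADA component includes seroconversion rate and time to seroconversion. Protocol 8.4 plans by-dose summaries of change from baseline in examination findings and ECG, among others, and adds: "All baseline and safety data collected during the study will be included in subject listings".

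SAP section 4 records the decision to stop development and says: "A clinical study report (CSR) will detail the final demographic, disposition, exposure and safety data of each study". SAP 4.1 says that the CSR outputs "represent a reduced subset of the overall total data analyses, data summaries, and data presentations" in the protocol, and that only the items in 4.1.4 will be included. The primary objective stays (4.1.1), and so does the endpoint in 5.2: "The primary endpoint of this study is the safety and tolerability of SBC-103 in subjects with MPS IIIB".

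The 4.1.4 list has no entry for ECG or physical examination. ECG is excluded again in 5.2.4.2 ("Analyses of electrocardiogram (ECG) data will not be included in the CSR") and 7.3.3.3.2 ("Analyses of ECG data will not be included in the CSR"). SAP 7.1.3.3 says: "Medical/surgical history and physical examination data will not be included in the CSR". For ADA, 4.1.4 has "Anti-drug Antibody (ADA) Assay and Titer Results". Neither seroconversion element appears in 4.1.4, 5.2, 7.3 or 7.3.3.3.1, either as kept or as dropped.

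**The concern.** A reader of SAP sections 4 to 4.1.3 learns that secondary and exploratory objectives are not addressed, that the primary objective is, and that the CSR will present the final safety data. That reader would expect the primary endpoint to be reported in full. It will not be.

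With at most 5 subjects and no inferential analysis, by-subject data are the main evidence on safety, so a missing listing is a real gap. What would go unseen is ECG and examination results not reported as AEs. These include the investigator's judgement of the clinical significance of each ECG abnormality (Protocol 5.1.7) and the abnormal examination findings recorded in the CRF (Protocol 5.1.5). For seroconversion, a reader would have to work out who converted and when, with no stated rule for a subject who was already positive before the first dose.

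**Working it through.** There is no plan figure to reproduce: the SAP gives no error rate, power or effect size, and the sample size is the size of the earlier study. The check sets the protocol components beside the SAP outputs and then counts scheduled assessments.

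**Step 1. Components (Protocol 3.4.1) against SAP outputs (4.1.4, 5.2, 7.3)**

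| Component | SAP output |
|---|---|
| AEs, SAEs, IARs | Tables and listing |
| ADA | Tables in part |
| Laboratory and CSF | Listing only |
| Vital signs | Listing only |
| Concomitant medications | Listing only |
| 12-lead ECG | None |
| Physical examination | None |

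Count: 1 in full + 1 in part + 3 listed + 2 absent = 7.

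**Step 2. Are ECG and examination really absent from listings?** The two ECG sentences exclude only analyses, so on their own they would leave room for a listing. SAP 4.1 closes that room: it applies to summaries and listings alike and admits only the 4.1.4 items. That list has 11 entries, none for ECG or examination. For examination, the sentence in 7.1.3.3 excludes the data themselves, but its heading refers to the baseline examination. On-treatment examination is therefore excluded mainly through the closed list.

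**Step 3. ADA elements.** The protocol component has six: seroconversion rate, time to seroconversion, titre by time point, peak titre, positive/negative status, and effect on safety. SAP 5.2 keeps the last four. 6 − 4 = 2 dropped.

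**Step 4. Scheduled assessments after first dose, through Week 12.** SAP section 7 says that all subjects were escalated after the first 12 weeks, so Week 12 is taken as reached by everyone. From Protocol 14.1 (repeated in SAP 9.1):

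- ECG: Screening and Day 0 (pre-dose) precede treatment; Week 12 follows it. Post-dose = 1.
- Examination: Screening and Day 0 (pre-dose) precede treatment; Day 1 and Weeks 4, 8 and 12 follow. Post-dose = 4.
- ADA: Day 0 (pre-dose) precedes treatment; Weeks 4, 8 and 12 follow. Post-dose = 3.

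The SAP does not give the number treated, so the range is 1 to 5 subjects:

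- ECG visits: 1 × 1 to 1 × 5 = 1–5
- Examinations: 4 × 1 to 4 × 5 = 4–20
- ADA samples: 3 × 1 to 3 × 5 = 3–15

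These are scheduled minimum counts. Pre-treatment values add 2 ECG visits, 2 examinations and 1 ADA sample per subject. ECG was best effort (Protocol 5.1.7), so completed ECGs may be fewer.

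**Step 5. Can seroconversion be recovered?** SAP 5.2.3 counts ADA among the laboratory assessments and promises listings of all laboratory results. SAP section 7 puts relative day on dated listings, with first dose as Relative Day 1, so days since first dose = relative day − 1. Nominal Weeks 4, 8 and 12 are Relative Days 29, 57 and 85, or 28, 56 and 84 days. First detection can thus be read to about 28 days, or finer where an extra sample was taken after an IAR. SAP 7.3.3.3.1 also tabulates confirmed status at each visit. Rate and time are therefore largely readable by hand; the definition and the summary line are missing.

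**The case against.** The best defence is that this is a declared scope decision. SAP 4.1 exists to record changes from the protocol, section 4 gives the reason, and the ECG exclusion is stated twice. Protocol 8.4 is text that the SAP expressly changes, so departing from it is not an inconsistency in itself. That stands as far as it goes: a reader might infer a concealed change to the primary endpoint, and the documents do not support that. But 4.1.1 and 5.2 present the primary objective and endpoint as retained, and no sentence says that components of it were cut. Nor does stopping the programme explain the selection: the SAP lists CSF-AI, a secondary endpoint in Protocol 3.4.2, and adds neutralising antibodies, which the protocol's ADA component does not mention.

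A second defence is that clinically significant findings are not lost. Protocol 7.1.1 makes unfavourable signs and worsening pre-existing conditions AEs, and 7.3 has related abnormal diagnostic results recorded under a diagnosis. This stands. A reader might infer that significant ECG or examination findings would vanish from the CSR; new or worsening ones should reach the AE tables and listings.

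A third is that, in treatment-naïve subjects, ADA incidence equals the seroconversion rate unless someone is positive before the first dose, and the Day 0 row would show that. This largely stands too, as step 5 shows.

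Finally, a reader might infer that seroconversion is the only item dropped without being named. The heading of 7.1.3.3 makes that insecure, since on-treatment examination may likewise be excluded only through the 4.1.4 list.

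**Conclusion.** The point holds as an incompletely reported primary endpoint in an openly reduced CSR. Two of seven components have no output at all, and a third lacks two of its six elements. The practical loss is mainly ECG and examination results not reported as AEs: at least 1 ECG visit and 4 examinations scheduled per subject after first dose through Week 12, plus pre-treatment values. The seroconversion gap is smaller, because by-visit status and the listings largely fill it. No inferential conclusion is affected, since none is planned. The change is worth making because it is cheap and lets the CSR report the endpoint it names.

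This rests on three readings: that the 4.1.4 list is closed, as 4.1 says; that every treated subject reached Week 12, as SAP section 7 says; and that ADA results are listed, as 5.2.3 implies.

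**What to change.** 1. Add two by-subject listings to SAP 4.1.4: ECG results with the investigator's clinical-significance judgement, and abnormal physical examination findings at all visits. Amend 5.2.4.2, 7.1.3.3 and 7.3.3.3.2 to match.
2. For seroconversion, do one of the following:
   - Add one line to 7.3.3.3.1: n/N of subjects negative at the pre-dose Day 0 sample who later have a confirmed positive, with days from first dose to the first positive (relative day − 1). Count the extra post-IAR samples, and show subjects positive at baseline separately.
   - Or name both elements in 4.1 as not reported, with the reason.

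The cost is SAP wording, two listings, and one simple derivation or one sentence, from assessments the protocol already schedules, in at most 5 subjects. The downside is a slightly longer abbreviated CSR.

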6. DATA SETS ANALYZED (STUDY POPULATIONS)

The following analysis sets will be used for the presentation and analysis of the data for the CSR. For further information on the processing of patient data utilized in creating the following study population analysis dataset(s)/subset(s) and baselines, please see Appendix 9.4.1.

6.1. Full Analysis Set (FAS)

Not applicable.

6.2. Per Protocol (PP) Set

Not applicable.

6.3. Safety Set

The Safety Analysis Set, defined as all patients for whom informed consent has been obtained, who have a confirmed diagnosis of MPS IIIB, and who have received any amount of SBC-103, will be used to summarize all safety and tolerability data.

6.4. Other Sets

Not applicable.

7. STATISTICAL ANALYSIS

All output will be sorted and labeled according to the International Conference on Harmonization (ICH) recommendations, and formatted to the appropriate page size(s).

For the analyses covered by this SAP, data analysis and presentation for this study is primarily descriptive in nature; therefore, no inferential analyses are planned. Selected data will be presented in by-patient data listings and summarized in tables across patients if appropriate.

SBC-103 1 mg/kg was administered qow for the first 12 weeks of study; the dose was then escalated to 3 mg/kg for all subjects. Descriptive summaries of data will be presented by the SBC-103 3 mg/kg qow dose group without regard to the initial treatment at the 1 mg/kg qow dose or any dose reductions. Continuous data will be summarized using descriptive statistics including number of patients, mean, standard deviation (SD), median, minimum, maximum, Lower quartile (25th percentile) Q1, and Upper quartile (75th percentile) Q3; categorical data will be summarized by counts and proportions. No formal statistical hypothesis testing will be performed.

For this analysis, information will be displayed as the SBC-103 3 mg/kg qow dose only except in treatment exposure and infusion listings. All data listings that contain an evaluation date will contain a relative study day (Rel Day). Pre-treatment and on-treatment study days are numbered relative to the day of the first dose of study drug which is designated as Relative Day 1. The preceding day is Day -1, the day before that is Day -2, etc. The last day of study drug is designated with an "L" (e.g., Day 14L).

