7.3.2. Adverse Events (AEs)

Information will be summarized on all AEs that began at any time from the date of first study procedure performed through the last procedure at the last study visit. Adverse events will be

classified by the study Investigator into one of the following relations to study drug: not related, unlikely related, possibly related or related to study drug. For reporting purposes, "related" events will include all AEs assessed by the Investigator as: possibly related or related to study drug.

All AEs captured in the eCRF will be coded using the Medical Dictionary for Regulatory Activities (MedDRA) coding system and displayed in tables and data listings using System Organ Class (SOC) and Preferred Term (PT). All AEs will be coded using the MedDRA, version 13.1 or higher.

Severity of AEs will be graded on a 3-point scale (mild, moderate and severe) based on the definitions, developed from Clinical Data Interchange Standards Consortium (CDISC) Study Data Tabulation Model (SDTM) standard terminology v3.1.1 (see Protocol Section 7.1.1).

Adverse event incidence will be reported based on the concept of treatment emergence for the purposes of this analysis. Any AE that occurs after the first dose of SBC-103 is considered a treatment emergent adverse event (TEAE) for this study.

Adverse events are summarized by patient incidence rates; therefore, in any tabulation, a patient contributes only once to the count for a given AE.

The number and percentage of patients with a TEAE will be summarized.

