7.3.2.5.2. Infusion-Associated Reactions

Infusion-associated reactions (IARs) will be considered AEs of special interest (AESIs). An AE will be considered an IAR if it meets either of the following criteria:

- The Investigator checks "Yes" to the question "Is AE an IAR?" on the AE eCRF.
- The AE (diagnosis and/or symptom) occurs between the start of the infusion up to 4 hours after the infusion and is assessed by the Investigator as at least possibly related to Investigational Medicinal Product (IMP).

Note that several AEs may be associated with 1 IAR observed with SBC-103 administration; each AE is captured as a separate event. The number and percentage of patients who experience any IAR and the number of IARs reported over the course of the study will be summarized. Any patient who experiences an IAR is only counted once regardless of the number of associated events. Patients may be counted more than once if IARs occur on more than 1 dosing day.

Summaries of AEs that comprise an IAR will be displayed by MedDRA PT. Each patient will be counted only once within each PT.

A by-patient data listing of all AEs will be presented.

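### SAP 7 heads every safety summary as 3 mg/kg qow although all subjects spent the first 12 weeks on 1 mg/kg, and the protocol's by-dose IAR incidence drops out without being named as a change

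*SAP*

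**What the plan says.** SAP 7 describes the dosing as it happened: "SBC-103 1 mg/kg was administered qow for the first 12 weeks of study; the dose was then escalated to 3 mg/kg for all subjects". The same paragraph then sets the display rule. Summaries are "presented by the SBC-103 3 mg/kg qow dose group without regard to the initial treatment at the 1 mg/kg qow dose", and any dose reductions are disregarded in the same way. It goes on to say that "information will be displayed as the SBC-103 3 mg/kg qow dose only except in treatment exposure and infusion listings", so the label also reaches the adverse event listings.

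Two counting rules fix what falls under that label. SAP 7.3.2 states: "Any AE that occurs after the first dose of SBC-103 is considered a treatment emergent adverse event (TEAE) for this study". For IARs, SAP 7.3.2.5.2 says that the number and percentage of patients with any IAR and "the number of IARs reported over the course of the study will be summarized".

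Protocol 8.4, repeated in the synopsis, planned that "incidence of IARs will be tabulated by dose and overall". SAP 4.1 says only that the CSR outputs "represent a reduced subset of the overall total data analyses, data summaries, and data presentations" described in the protocol. SAP 4.1.4 then lists what is kept. Several items there are marked as listings only. IARs appear with no qualifier.

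**The concern.** The header names one dose, and the data beneath it come from at least two. Safety and tolerability is the only objective this SAP keeps (SAP 4.1.1 to 4.1.3), so these tables are the main product of the CSR. A reader who takes a table headed 3 mg/kg qow at face value will credit that dose with every event since the first infusion, including any that arose at 1 mg/kg or after a reduction.

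IARs are where this matters most. Under the timing criterion an IAR "occurs between the start of the infusion up to 4 hours after the infusion", so it belongs to one infusion and one known dose. The protocol asked for exactly that split. With the split gone and the single-dose header in its place, no planned table shows whether IARs began at the starting dose or only after escalation.

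**Working it through.** No sample-size, power or alpha figure is involved, so there is no figure of the plan's own to reproduce. The check is a comparison of texts plus simple arithmetic on exposure.

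**1. Does a 1 mg/kg event land under the 3 mg/kg header?** Take an IAR at the second infusion (Week 2).
- Dose given: 1 mg/kg (SAP 7).
- Treatment-emergent: yes, because it follows the first dose (SAP 7.3.2).
- In the IAR summary: yes, because that covers the whole study (SAP 7.3.2.5.2).
- Column header: 3 mg/kg qow (SAP 7).

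The same holds for an event at a reduced dose.

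**2. Is the protocol's by-dose IAR incidence produced anywhere?** The SAP's IAR outputs are an overall count and percentage, a breakdown by preferred term (both 7.3.2.5.2), and a table by system organ class, preferred term and ADA positivity (7.3.3.3.1). None is split by dose. The *overall* half of the protocol's table survives, under the wrong header. The *by dose* half does not.

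**3. Is the loss named?** SAP 4.1 gives a general notice. SAP 4.1.4 marks laboratory data and vital signs, which Protocol 8.4 also planned by dose, as listings only, so their reduction is visible. IARs carry no such mark.

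**4. How much exposure is affected?** Infusions are every 2 weeks from Day 0. The number through Week T is T/2 + 1.
- At 1 mg/kg: Weeks 0 to 10 give 10/2 + 1 = 6. If Week 12 was also at 1 mg/kg, 12/2 + 1 = 7. Seven is plausible because the escalation review uses the 12-week CSF HS result (Protocol 3.3.2), and that CSF is drawn pre-dose at the Week 12 visit (Protocol Appendix A).
- Planned total: 156/2 + 1 = 79.
- Actual treatment length is not stated. SAP 4 gives only the date of the decision to stop the programme, so shorter lengths are assumptions.

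| Treatment length | Infusions | 6 at 1 mg/kg | 7 at 1 mg/kg |
|---|---|---|---|
| 156 weeks (planned) | 79 | 7.6% | 8.9% |
| 104 weeks (assumed) | 53 | 11.3% | 13.2% |
| 52 weeks (assumed) | 27 | 22.2% | 25.9% |

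These are shares of infusions per subject with none missed and no dose reduced. They are not shares of events.

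**5. What can one subject do to a rate?** With N = 5, the planned maximum, a subject whose only event arose at 1 mg/kg adds 1/5 = 20 percentage points to an incidence headed 3 mg/kg.

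**The case against.** The best defence is that nothing is hidden. SAP 7 states the 1 mg/kg phase, the escalation, the pooling and the exception for exposure listings in plain words. All subjects were escalated, so the header can be read as naming a group of subjects by target dose, not the dose at onset. The programme has been stopped, the CSR is abbreviated, and SAP 4.1 says the outputs are reduced. With at most five subjects, anyone can match the relative day in the AE listing to the target dose by visit in the dosing listing. A by-dose table would set 6 or 7 infusions per subject against several times as many, with dose fully confounded with time on drug.

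Much of this stands. The fault is an inaccurate header and an unnamed departure, not concealment. The confounding is real and limits what a by-dose table can show. But disclosure in the SAP does not correct the header on a CSR table. Reconstruction by hand is not a planned output. One treatment group justifies a pooled column, but not one named for a single dose.

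A reader might go further and infer that events at 1 mg/kg were sought harder, so that the pooled rate is biased by closer early follow-up. The 24-hour in-patient stay after dose 1 and the calls after doses 2, 3 and 4 do fall in the 1 mg/kg phase. However, Protocol Table 2 also schedules draws at 8, 12 and 24 hours after the Week 24 infusion, which on SAP 7's account follows escalation (the 24-hour draw may be omitted for blood volume). Protocol 7.3 has AEs sought at every contact. Protocol 5.1.7 keeps infusion vital-sign monitoring the same until Week 54. The documents do not support a claim that all extra follow-up sits at 1 mg/kg.

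**Conclusion.** The point holds for the header and for the IAR table. By the SAP's own rules, events at 1 mg/kg or at a reduced dose are reported as 3 mg/kg incidence, and the protocol's by-dose IAR incidence is lost without being named. The exposure concerned is 6 or 7 infusions per subject: 7.6–8.9% of the planned schedule, and more if treatment was shorter. The 104- and 52-week figures rest on assumed durations and are illustrations, not bounds. The documents do not say how many events are affected or whether any dose was reduced. The 20-point figure is conditional on N = 5 and on such a subject existing.

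Two wider readings are tempting but not supported. One is that the protocol promised AE and SAE tables by dose. Protocol 8.4 says *across doses* for these, which can mean pooled, and the *dose cohort* wording of Protocol 8.1 is ambiguous in a study with one treatment group (Protocol 6.4). The other is that the IAR-by-ADA table should be split by dose. The protocol asks for the relationship between ADA and IARs, not for that split, so only its header needs correcting.

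**What to change.** - Rename the pooled column *All SBC-103 (any dose)* in every table and listing that now carries the 3 mg/kg label.
- Tabulate IARs by dose and overall, assigning each to the dose of the infusion at onset or last before it. Give the subjects and infusions exposed at each dose as denominators, since exposure is otherwise only listed.
- Add that derived dose to the AE and IAR listings.
- State that by-dose counts are descriptive only, because under fixed-order escalation dose is confounded with time on drug.
- Name in SAP 4.1 any protocol by-dose summary that is still not produced.

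The cost is some SAP wording, a header change, one table and one variable derived from infusion data already being listed. The downside is a few sparse columns. For IARs designated by the Investigator outside the 4-hour window, the last-infusion rule is a convention and should be described as one.
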